### 3.1    **Study design**

This non-confirmatory study will be conducted in 2 cohorts using a one-sequence two-period design to compare SOM230 vs. Placebo. Following observed efficacy and safety signals in Cohort 1 with the 1.5 mg dose, cohort 2 of the study assessing efficacy of a lower SOM230 dose (0.9 mg) may be considered.

Two consecutive attacks will be treated: first attack will be treated with placebo (Period 1) and the following attack will be treated with SOM230 (Period 2). Approximately 30 patients will be enrolled in Cohort 1 to receive Placebo s.c. single dose in Period 1 then SOM230 1.5 mg s.c., a single dose in Period 2. Each study cohort will consist of a 21 day screening period, a baseline period of 3 days prior to the Baseline Visit, a treatment period (Period 1) lasting up to 3 days then a treatment period 2 of up to 3 days, followed by an end of study visit 3 days after study drug administration in Period 2. The subjects will have up to 5visits. Similarly, in Cohort 2 approximately 30 subjects will receive placebo s.c. single dose in Period 1 and SOM230 0.9 mg s.c., as a single dose in Period 2. Each subject will be instructed to self-administer (or assisted by a helper, or by medical staff if domiciled at a clinic) the study medications at the beginning of the CH attack (as early as possible; within 10 minutes of start of attack when pain is at least moderate). In case patient experiences CH attacks PRIOR to administering study treatment in Period 1 they can use 100% O2 or their conventional treatment to manage their acute attacks experienced before Period 1. If the subject does not have a headache attack in **72 hours post-baseline** or 72 hours post Period 1 treatment the subject will be excluded from the study. Subjects will be required to complete a patient diary to document the pain severity and pain relief before and after the administration of the study medication (**Figure 3-1**). In case the pain is not responding to the administered study drug after 30 minutes, subjects will be allowed to use only 100% oxygen as a rescue

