### 4.1 Inclusion criteria

1. Subject is male or female age 18-65 inclusive.
2. Written informed consent must be obtained before any assessment is performed.
3. Subjects must have established diagnosis of episodic cluster headaches (CH) or chronic CH, averaging 2-6 headache attacks per day each lasting at least 45 minutes without treatment, not to exceed 6 attacks per day within the last year.
4. Able to communicate well with the investigator, to understand and comply with the requirements of the study, as well as accepting NOT to share any study information through social media during their participation in the study.
5. Subject is able to self-inject medication subcutaneously or have the assistance of a helper on an out-patient basis, if subject is not domiciled in a clinic for the study.

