All adverse events should be treated appropriately. Treatment may include one or more of the following:

- no action taken (i.e. further observation only)
- study treatment dosage adjusted/temporarily interrupted
- study treatment permanently discontinued due to this adverse event
- concomitant medication given
- non-drug therapy given
- subject hospitalized/subject's hospitalization prolonged

Once an adverse event is detected, it should be followed until its resolution or until it is judged to be permanent, and assessment should be made at each visit (or more frequently, if necessary) of any changes in severity, the suspected relationship to the study drug, the interventions required to treat it, and the outcome.

Information about common side effects already known about the investigational drug can be found in the Investigator Brochure (IB) or Core Data Sheet (for marketed drugs) or will be communicated between IB updates in the form of Investigator Notifications. This information will be included in the subject informed consent and should be discussed with the subject during the study as needed.

The investigator should also instruct each subject to report any new adverse event (beyond the protocol observation period) that the subject, or the subject's personal physician, believes might reasonably be related to study treatment. This information should be recorded in the investigator's source documents, however, if the AE meets the criteria of an SAE, it must be reported to Novartis.

If required by a local regulatory authority, the investigator will identify and declare a consulting endocrinologist to review relevant Adverse Events.

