## 9.2 Serious adverse event reporting

### 9.2.1 Definition of SAE

An SAE is defined as any adverse event (appearance of (or worsening of any pre-existing) undesirable sign(s), symptom(s) or medical conditions(s) which meets any one of the following criteria:

- is fatal or life-threatening
- results in persistent or significant disability/incapacity
- constitutes a congenital anomaly/birth defect
- requires inpatient hospitalization or prolongation of existing hospitalization, unless hospitalization is for:
  - routine treatment or monitoring of the studied indication, not associated with any deterioration in condition of cluster headache elective or pre-planned treatment for a pre-existing condition that is unrelated to the indication under study and has not worsened since the start of study drug
  - treatment on an emergency outpatient basis for an event not fulfilling any of the definitions of a SAE given above and not resulting in hospital admission
  - social reasons and respite care in the absence of any deterioration in the patient's general condition
- is medically significant, i.e. defined as an event that jeopardizes the subject or may require medical or surgical intervention to prevent one of the outcomes listed above.

Life-threatening in the context of a SAE refers to a reaction in which the subject was at risk of death at the time of the reaction; it does not refer to a reaction that hypothetically might have caused death if more severe.

All malignant neoplasms will be assessed as serious under "medically significant" if other seriousness criteria are not met.

Any suspected transmission via a medicinal product of an infectious agent is also considered a serious adverse reaction.

Medical and scientific judgment should be exercised in deciding whether other situations should be considered serious reactions, such as important medical events that might not be immediately life threatening or result in death or hospitalization but might jeopardize the patient or might require intervention to prevent one of the other outcomes listed above. Examples of such events are intensive treatment in an emergency room or at home for allergic bronchospasm, blood dyscrasias or convulsions that do not result in hospitalization or development of dependency or abuse.

All AEs (serious and non-serious) are captured on the CRF, SAEs also require individual reporting to DS&E as per [Section 9.2.2](#).

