### **9.2.2 SAE reporting**

To ensure subject safety, every SAE, regardless of causality, occurring after the subject has provided informed consent and until 30 days after the last study visit, must be reported to Novartis within 24 hours of learning of its occurrence as described below. Any SAEs experienced after this should only be reported to Novartis if the investigator suspects a causal relationship to study treatment.

Recurrent episodes, complications, or progression of the initial SAE must be reported as follow-up to the original episode, regardless of when the event occurs. This report must be submitted within 24 hours of the investigator receiving the follow-up information. An SAE that is considered completely unrelated to a previously reported one should be reported separately as a new event.

Information about all SAEs (either initial or follow up information) is collected and recorded on the paper Serious Adverse Event Report Form. The investigator must assess the relationship to each specific component of study treatment (if study treatment consists of several drugs) complete the SAE Report Form in English, and send the completed, signed form by fax within 24 hours after awareness of the SAE to the local Novartis Drug Safety and Epidemiology Department, notifying the Clinical Trial Leader. Contact information is listed in the Site Operations Manual.

The original copy of the SAE Report Form and the fax confirmation sheet must be kept with the source documentation at the study site. Follow-up information should be provided using a new paper SAE Report Form stating that this is a follow-up to a previously reported SAE.

SAEs (initial and follow-up) that are recorded electronically in the Electronic Data Capture system should be entered, saved and e-signed within 24 hours of awareness of the SAE or changes to an existing SAE. These data will automatically be submitted to Novartis Drug Safety & Epidemiology immediately after investigator signature or 24 hours after entry, whichever occurs first. Study site personnel must also inform the Clinical Trial Leader.

Follow- up information provided should describe whether the event has resolved or continues, if and how it was treated, whether the treatment code was broken or not and whether the subject continued or withdrew from study participation. Each re-occurrence, complication, or progression of the original event should be reported as a follow-up to that event regardless of when it occurs.

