#### **Adverse events**

All information obtained on adverse events will be displayed by treatment and subject.

The number and percentage of subjects with adverse events will be tabulated by body system and preferred term with a breakdown by cohort and treatment. An adverse event starting in one period and continuing into the next period is counted only in the onset period. A subject with multiple adverse events within a body system is only counted once towards the total of this body system and treatment.

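### The onset-period rule for adverse events has no exception for worsening, so an event that worsens after the SOM230 dose can be tabulated under placebo only

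*SAP*

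**What the plan says.** The SAP (7.1.2, Adverse events) plans a table of the number and percentage of subjects with adverse events, by body system and by preferred term, split by cohort and treatment. For events that span the two periods it states: "An adverse event starting in one period and continuing into the next period is counted only in the onset period". Protocol 11.5.2 has the same sentence. Neither document has a visible definition of a treatment-emergent event, and neither says where an event is counted if it worsens after the second dose.

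The order of treatment is fixed (Protocol 3.1): "first attack will be treated with placebo (Period 1) and the following attack will be treated with SOM230 (Period 2". Section 3.1 also caps the gap between the doses: with no attack in "72 hours post Period 1 treatment the subject will be excluded from the study".

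On recording, Protocol 9.1 has each event followed until it resolves or is judged permanent, and says that "assessment should be made at each visit (or more frequently, if necessary) of any changes in severity, the suspected relationship to the study drug" and other features. Once an event is an SAE, Protocol 9.2.2 says: "Recurrent episodes, complications, or progression of the initial SAE must be reported as follow-up to the original episode, regardless of when the event occurs". The SAE definition in 9.2.1 begins with "appearance of (or worsening of any pre-existing) undesirable sign(s), symptom(s) or medical conditions(s", so it covers worsening as well as first appearance.

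**The concern.** In a crossover with both treatment orders, an onset-period rule can misplace a worsened event in either direction. Here no subject takes placebo after SOM230. Between treatments the rule can therefore only leave a worsened event on placebo; it can never leave one on SOM230.

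For an event that continues unchanged this is correct, because it began under placebo. The difficulty is confined to an event that starts after placebo and then rises in grade, or becomes serious, after SOM230. The worsening is new information about SOM230, yet the rule gives SOM230 no event. Safety and tolerability of SOM230 is a secondary objective, and this table is its main numerical summary of adverse events.

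**Working it through.** The plan states no AE rate, so there is no figure of its own to reproduce. The check traces the rule through the possible cases and then sizes one misplaced subject.

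**Inputs.** Counting rule: SAP 7.1.2 and Protocol 11.5.2. Treatment order and 72-hour cap: Protocol 3.1. Attack rate: Protocol 4.1, "averaging 2-6 headache attacks per day each lasting at least 45 minutes without treatment". Cohort size: about 30 enrolled (Protocol 3.1, SAP 1.4) and 23 evaluable (Protocol 11.6). These two agree: 23 / (1 − 0.20) = 28.75, which rounds up to 29.

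**Step 1: trace the rule.**

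| Event | Counted under | Correct? |
|---|---|---|
| Starts after placebo, ends before SOM230 | Placebo | Yes |
| Starts after placebo, continues unchanged | Placebo | Yes |
| Starts after placebo, worsens after SOM230, one record | Placebo only | No: the worsening is not counted under SOM230 |
| Starts after placebo, worsens after SOM230, new record opened | Placebo, then SOM230 | Yes |
| Starts after SOM230 | SOM230 | Yes |

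Only the third row is a problem, and it depends on how worsening is recorded.

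**Step 2: which recording does the text suggest?** Protocol 9.1 treats a change in severity as something observed within an event already being followed. Section 9.2.2 treats progression of an existing SAE as follow-up. No visible text opens a new record on worsening. The natural reading is one record with a Period 1 onset. For a non-serious Period 1 event that becomes serious after SOM230, 9.2.1 makes it reportable as an SAE, but nothing states whether its onset date changes.

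**Step 3: can an event span both doses?** At 2 to 6 attacks a day the mean gap between attacks is 24/6 = 4 hours to 24/2 = 12 hours. If attacks followed a Poisson process (an assumption), the chance that the next attack comes within t hours is 1 − exp(−r·t/24):

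- t = 6: 1 − exp(−0.5) = 0.393 at r = 2; 1 − exp(−1.5) = 0.777 at r = 6.
- t = 24: 1 − exp(−2) = 0.865 at r = 2; 1 − exp(−6) = 0.998 at r = 6.

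The 6- and 24-hour event durations are assumed too. These figures show that overlap is plausible. They are not probabilities of worsening or of misattribution.

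**Step 4: size per subject.** If the subject has no other SOM230 event of that term, the SOM230 percentage for the term is too low by 1/30 = 3.3 points, or 1/23 = 4.3 points. The placebo count is right either way, because onset was under placebo.

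**Step 5: how many subjects?** Let q be the share of subjects with a Period 1 event that persists and worsens after SOM230. The documents do not give q; the range below is assumed. The expected number is n·q, and the chance of at least one is 1 − (1 − q)^n.

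| q | n = 30: expected | n = 30: at least one | n = 23: expected | n = 23: at least one |
|---|---|---|---|---|
| 1% | 0.3 | 0.260 | 0.23 | 0.206 |
| 2% | 0.6 | 0.455 | 0.46 | 0.372 |
| 5% | 1.5 | 0.785 | 1.15 | 0.693 |
| 10% | 3.0 | 0.958 | 2.3 | 0.911 |

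**The case against.** The strongest reply is that the sentence is an ordinary guard against double counting. It speaks of an event that continues, and does not say that a worsening counts as continuing. Recording methods are left to the Site Operations Manual, and the AE form is not visible either. If either opens a new record on worsening, the new record has a Period 2 onset and is counted under SOM230. The mention of worsening in 9.2.1 gives some support to that reading for events that become serious. This stands as a condition on the point. It does not remove it, because the visible text in 9.1 points to a single record and the counting rule has no exception.

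A reader might go further in four ways that the documents do not support.

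- *SOM230 toxicity is understated overall.* Not shown. SOM230 is followed to the end-of-study visit three days after dosing, with safety contact for a further 30 days; placebo has at most 72 hours before the next dose. Late placebo-related or background events that begin in Period 2 count against SOM230. These effects push the other way, though they do not put a misplaced event back.
- *Severity under placebo is inflated.* The planned table has no stated severity breakdown.
- *The rule contradicts 9.1 and 9.2.1.* Those sections govern follow-up and reporting, not tabulation. They are not aligned with the rule, but they do not conflict with it.
- *The move to Cohort 2 is distorted.* The visible criteria in Protocol 7.4 rest on related SAEs, on investigator and sponsor judgement, and on an observed safety signal. None refers to this table.

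The listing of all AE information and the individual SAE reports would still show the event. That limits the harm but does not correct a percentage. Also, a fresh reaction to the Period 2 injections starts in Period 2 and already counts under SOM230.

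**Conclusion.** The point holds in a limited form. The written rule can attribute a SOM230-period worsening to placebo alone, and with the fixed order this particular error runs in one direction only. It rests on one assumption: that a worsening stays in the Period 1 record. The visible text suggests this but does not settle it.

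The effect is on one descriptive incidence table in a non-confirmatory study. The 3.3 or 4.3 points per subject apply to a preferred-term row. A body-system row moves only if the subject has no other SOM230 event in that body system. The number of subjects affected is unknown, so no total bias can be stated. The change is worth making because attribution is least clear for events that become worse or serious after the active dose, and the repair is small.

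**What to change.** Amend the Adverse events text in SAP 7.1.2 and Protocol 11.5.2. An event that continues into Period 2 unchanged stays in its onset period only. An event that increases in grade or becomes serious after the Period 2 dose is also counted under SOM230.

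To make this workable, either record the date of each grade change (and of becoming serious) on the AE form, or instruct sites to open a new AE record on worsening. State the choice in Protocol 9.1 so that recording and tabulation agree.

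The cost is one sentence in each document and one more date on the AE form, or a recording instruction in its place. A few subjects may appear under both treatments, and the SOM230 AE rate may look slightly less favourable. Treatment and clinical follow-up are unaffected.

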### **7.1.3 Graphical presentation**

Boxplots to visualize trends in longitudinal safety data (vitals) will be created.
